1 INTRODUCTION

1.1 Background

Traumatized patients frequently experience pain prehospital due to the fear of adverse cardiovascular effects (e.g. hypotension) and respiration depression of opioid treatment, leading to insufficient analgesia.(1,2) Therefore, there is of interest to investigate other analgesics that do not have these adverse effects.

In Norway, methoxyflurane has been approved for the emergency relief of moderate to severe trauma pain in conscious adult patients. Methoxyflurane (Penthrox®) do not have these adverse effects (hypotension and respiration depression). It is easy to administrate via an inhalator, and is therefore suitable for use prehospital. This would possible help to treat pain better prehospital.

There exists no data of how effective methoxyflurane is as an analgesic compared to an opioid. The aim of this study is to determinate the equipotent doses of inhaled methoxyflurane vs. intravenous fentanyl.

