5.4 Premedication and Monitoring

No premedication will be used.

Vital sign assessment (blood pressure and respiration frequency) will be registered during each session.

Continuous ECG, heart rate, ETCO2 and SpO2 measurement will be registered throughout each session.

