7.2 Safety and Tolerability Assessments

Safety will be monitored by the assessments described below as well as the collection of AEs at every session. Significant findings that are present prior to the signing of informed consent must be included in the relevant medical history/ current medical condition page of the CRF. For details on AE collection and reporting, refer to Section 8.

Pulsoxymetry, ETCO₂ and ECG will be continuously monitored during the study. Necessary acute medical equipment is available (Lærdalsbag, suction, intravenous liquid, naloxone. In addition anesthetic drugs: adrenalin, atropine and ephedrine).

Side effects will be recorded: sedation, dizziness, itching, nausea and vomiting. Respiration frequency and non-invasive blood pressure will be recorded every 5. min

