8.1 Definitions

8.1.1 Adverse Event (AE)

An AE is any untoward medical occurrence in a patient administered a pharmaceutical product and which does not necessarily have a causal relationship with this treatment.

An adverse event (AE) can therefore be any unfavorable and unintended sign (including an abnormal laboratory finding), symptom, or disease temporally associated with the use of a medicinal (investigational) product, whether or not related to the medicinal (investigational) product.

The term AE is used to include both serious and non-serious AEs.

AE that do not need to be recorded (expected AE): for opioid (fentanyl): sedation, dizziness, itching, nausea and vomiting are frequent AE's. If the AE's are mild and/or acceptable for the subject, the subject will not be excluded from the study and the AE do not need to be recorded. Mild respiration depression (resp frequency > 8/min) will be accepted as AE that do not need to be recorded.

If an abnormal laboratory value/vital sign are associated with clinical signs and symptoms, the sign/symptom should be reported as an AE and the associated laboratory result/vital sign should be considered additional information that must be collected on the relevant CRF.

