8.2 Expected Adverse Events

The following side-effects/adverse events: respiratory depression, sedation, nausea, vomiting, pruritus, dizziness and headache will be registered in the CRF.

Such AEs will be registered in the AE/SAE section of the CRF. Further adverse events listed in the SmPCs for the study drugs will also be registered as AE/SAE if they occur

- 1) Pentrox® 3 ml / ATC-nr. N02B G09/ Inhalation vapour, Mundipharma, Norwegian version section 4 "Bivirkninger".
- 2) Fentanyl® 2 ml, 0.05 mg/ml /ATC-nr. N01A H01/ intravenous use, Hameln, Norwegian version section 4 "Bivirkninger".

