8.5.4 Clinical Study Report

The adverse events and serious adverse events occurring during the study will be discussed in the safety evaluation part of the Clinical Study Report.

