10.5 Statistical Analysis

10.5.1 Primary analysis and Secondary analysis

The linear mixed-model procedure will be used to compare the effect of different treatments in the NRS in the cold-pressor pain model. This is a variance component model that takes into account correlations/dependence as a result of repeated treatments, carryover effects, and repeated observations in each treatment session on each subject. This statistical analysis is appropriate for a crossover study with repeated measurements.

The dependent variables were changes from baseline in the NRS in the cold-pressor pain model. For all analyses, pairwise comparisons between the treatments will be made only if the overall test for the difference between all treatments was significant at the level of 0.05. This Fisher's least significant difference method provides protection for multiple comparisons. Data will be analyzed in SPSS.

The primary endpoint is NRS during CPR at time zero

The secondary endpoint is NRS during CPR at time 15 min

Statistical hypothesis test:

- Null hypothesis: The difference in pain between the treatment (metoxyflurane) is at least 0.5 point on the 0-10 NRS scale in favor of the control treatment (fentanyl 0.05 mg).
- Alternative hypothesis: The difference in pain between the treatment (metoxyflurane) is less than 0.5 point on the 0-10 NRS scale in favor of the control treatment (fentanyl 0.025 mg).

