10.5.2 Safety analyses

The safety analyses population will include all subjects who completed all 4 treatments.

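### Respiration and blood pressure are measured under all four treatments, but no planned analysis uses them and nothing requires a between-drug difference short of an adverse event to be reported

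*Combined protocol and SAP*

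**What the plan says.** **Rationale.** Sections 1.1 and 1.3 start from under-treatment of pain because opioids are feared to lower blood pressure and depress respiration. Section 1.1 then states: "Methoxyflurane (Penthrox®) do not have these adverse effects (hypotension and respiration depression").

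**Measurement.** Section 7.2: "Respiration frequency and non-invasive blood pressure will be recorded every 5. min". Section 5.4: "Continuous ECG, heart rate, ETCO2 and SpO2 measurement will be registered throughout each session". Under section 5.3 each volunteer is to receive all four treatments, so the readings are paired within volunteer.

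**Analysis.** Section 10.5.1 specifies the mixed model for one kind of outcome: "The dependent variables were changes from baseline in the NRS in the cold-pressor pain model". The complete text of 10.5.2 is "The safety analyses population will include all subjects who completed all 4 treatments". It names no variable, summary or comparison. Section 10.4 leaves further detail of the planned analyses to a separate SAP.

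**Reporting.** Section 8.5.4: "The adverse events and serious adverse events occurring during the study will be discussed in the safety evaluation part of the Clinical Study Report". On which respiratory events are written down, two sections differ. Section 8.1.1: "Mild respiration depression (resp frequency > 8/min) will be accepted as AE that do not need to be recorded". Section 8.2, with no threshold: "The following side-effects/adverse events: respiratory depression, sedation, nausea, vomiting, pruritus, dizziness and headache will be registered in the CRF".

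**The concern.** The trial seeks the fentanyl dose that matches 3 ml methoxyflurane for pain relief. Its clinical interest, by its own rationale, is that methoxyflurane might give that relief without the respiratory and circulatory cost of an opioid. The crossover collects the data to estimate that cost in the same people at the same doses, and then plans no use of them.

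If the plan is followed as written, the report could state equipotency on NRS and list few or no respiratory or hypotensive events. A reader could take such a list as support for the premise in 1.1. It would be weak support from 12 volunteers, while more informative readings would sit in the CRF unreported.

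**Working it through.** **1. The plan's only computed figure.** Section 10.1 gives n = 10 for 80% power to detect 0.5 NRS points with an SD of differences of 0.5 (paired t-test, two-sided 0.05). From the noncentral t with noncentrality √n × 0.5/0.5, n = 10 gives power 0.803 and n = 9 gives 0.748, so the figure reproduces. The 12 enrolled give 0.883. This concerns pain only; nothing is sized for respiration or blood pressure.

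**2. Each measurement followed to its use.**

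| Variable | Collected | In a planned analysis | Stated route to the report |
|---|---|---|---|
| NRS | three cold pressor tests per session (6.1) | yes (10.5.1) | main result |
| Respiratory rate | every 5 min (7.2) | none | only as an AE or SAE (8.5.4) |
| Blood pressure | every 5 min (7.2) | none | only as an AE or SAE (8.5.4) |
| ETCO2, SpO2 | continuously (5.4) | none | only as an AE or SAE (8.5.4) |

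**3. What event counts can show with n = 12.**
- Upper bound on the true risk after 0 events in 12: one-sided 95%, 1 − 0.05^(1/12) = 0.221; two-sided 95%, 1 − 0.025^(1/12) = 0.265.
- Exact McNemar test of one treatment pair: five discordant volunteers, all in one direction, give 2 × 0.5^5 = 0.0625; six give 2 × 0.5^6 = 0.031. At least six one-way discordant volunteers out of 12 are needed for p < 0.05.

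**4. What the readings can show.** The 95% CI half-width for a paired mean difference is t(0.975, n−1) × SD/√n, where SD is that of the paired differences.
- n = 12: 2.201/3.464 = 0.635 × SD.
- Withdrawn volunteers are not replaced (6.4.1). With n = 11, 10 or 9 the factor is 0.672, 0.715 or 0.769.
- The documents give no SD for respiratory rate. For assumed SDs of 1, 2, 3 and 4 breaths/min, n = 12 gives half-widths of 0.6, 1.3, 1.9 and 2.5 breaths/min.

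The planned mixed model uses all four treatments, so its intervals may differ somewhat from this simple paired calculation.

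**5. Which readings are usable.** Sections 6.1 and 6.2.2 instruct 10 breaths through the inhaler over about 1 to 1.5 minutes, which is 10/1.5 = 6.7 to 10/1 = 10 breaths/min in every arm, placebo included. A lowest rate taken over the whole post-dose period could simply record that instruction. The immersions at times 0 and 15 last up to 90 seconds, so readings there are taken in pain. If the 5-minute grid follows the session clock (an assumption), the readings at 5 and 10 minutes and those from 20 minutes on avoid the immersions. Those two sections also have the inhaled dose finished before time zero.

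**The case against.** **The separate SAP may cover it.** Its contents are not in the documents, so its silence cannot be shown. But section 10.4 promises detail on planned analyses, and the protocol plans none for these variables. This limits the claim to what the plan requires.

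**Respiratory depression does have a reporting route.** This stands, and it rules out a stronger reading. A reader might infer that any respiratory difference staying above 8 breaths/min would go unreported. The documents do not support that. Section 8.2 registers respiratory depression without a threshold. The wording in 8.1.1 permits non-recording rather than forbidding recording, concerns rate only, and stands in a paragraph introduced for fentanyl. The same section requires abnormal vital signs linked to symptoms to be collected. Section 8.6 has SpO2 triggers that do not depend on rate. All of these yield events, however; none yields a comparison of the readings between treatments.

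**Respiration is not an endpoint.** True. The sole aim is equipotent analgesia, and section 7.3 presents monitoring as a way to detect severe adverse effects. That argues for exploratory estimation rather than a new hypothesis test, and against treating the gap as a flaw in the primary result. It does not justify leaving paired data unused on the harms given as the trial's motive.

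**Conclusion.** The omission is established by the text. Four safety variables are measured under all four treatments, none enters an analysis, and safety reporting is described only as AEs and SAEs. Nothing in the plan therefore requires a respiratory or blood pressure difference between the drugs to be reported unless it is itself an AE.

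The size can be stated without respiratory data: zero events in 12 still allows a risk of 22% (one-sided) or 26% (two-sided), against a paired interval of about ±0.64 SD. This assumes 12 completers and roughly normal paired differences.

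It would be tempting to add a power comparison between threshold counts and measured rates. The documents give no mean, SD or expected fall for respiration, and the chance of at least one low reading depends on how many readings each session yields. Such a figure would be set by the chosen inputs, and the conclusion does not need it.

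The gap merits a change before database lock; it does not affect the NRS analysis.

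**What to change.** Add an exploratory analysis to 10.5.2, outside the error control for NRS:

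- **Outcomes:** change from the last pre-dose reading in respiratory rate, ETCO2, SpO2 and blood pressure.
- **Readings:** prespecified post-dose times outside both the instructed inhalation and the immersions, for example 5 and 10 minutes and those after the last cold pressor test. The timeline table labels inhalation continuous, so confirm when it ends before fixing the times.
- **Comparison:** methoxyflurane against each fentanyl dose and against placebo, using the mixed model already planned, with mean differences and 95% confidence intervals.
- **Population:** all dosed subjects, as in the 10.3 safety population. The completers-only set in 10.5.2 conflicts with 10.3 and would drop anyone withdrawn for an adverse effect under 6.2.4.
- **Table:** number of volunteers, by treatment, meeting the thresholds already in 8.6, marking any that occur during the instructed breaths.

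State in 8.5.4 that these results are reported with the AEs. Sections 8.1.1 and 8.2 must be reconciled on recording respiratory depression; no clinical threshold or management rule is proposed here.

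**Cost:** a few sentences in 10.5.2, 8.5.4 and the SAP, and some data entry. Sections 5.4 and 7.3 say ETCO2 and SpO2 are registered, while 6.1 and 7.2 say only monitored, so the CRF should require their values at the chosen times. There will be a few more exploratory comparisons, and the intervals at n = 12 will be wide. No new measurement or volunteer is needed.

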11 STUDY MANAGEMENT

11.1 Investigator Delegation Procedure

The principal investigator is responsible for making and updating a "delegation of tasks" listing all the involved co-workers and their role in the project. He will ensure that appropriate training relevant to the study is given to all of these staff, and that any new information of relevance to the performance of this study is forwarded to the staff involved.

11.2 Protocol Adherence

Investigators ascertain they will apply due diligence to avoid protocol deviations. All significant protocol deviations will be recorded and reported in the Clinical Study Report (CSR).

11.3 Study Amendments

If it is necessary for the study protocol to be amended, the amendment and/or a new version of the study protocol (Amended Protocol) must be notified to and approved by the Competent Authority and the Ethics Committee according to EU and national regulations.

11.4 Audit and Inspections

Authorized representatives of a Competent Authority and Ethics Committee may visit the centre to perform inspections, including source data verification. Likewise the representatives from sponsor may visit the center to perform an audit. The purpose of an audit or inspection is to systematically and independently examine all study-related activities and documents to determine whether these activities were conducted, and data were recorded, analyzed, and accurately reported according to the protocol, Good Clinical Practice (ICH GCP), and any applicable regulatory requirements. The principal investigator will ensure that the inspectors and auditors will be provided with access to source data/documents.

12 ETHICAL AND REGULATORY REQUIREMENTS

The study will be conducted in accordance with ethical principles that have their origin in the Declaration of Helsinki and are consistent with ICH/Good Clinical Practice and applicable regulatory requirements. Registration of patient data will be carried out in accordance with national personal data laws.

12.1 Ethics Committee Approval

The study protocol, including the patient information and informed consent form to be used, must be approved by the regional ethics committee before enrolment of any patients into the study. The application deadline for REC South East will be 11.12.2018.

The investigator is responsible for informing the ethics committee of any serious and unexpected adverse events and/or major amendments to the protocol as per national requirements.

12.2 Other Regulatory Approvals

The protocol will be submitted and approved by the applicable competent authorities before commencement of the study:

The protocol will also be registered in www.clinicaltrials.gov and kliniskestudier.helsenorge.no before inclusion of the first subject.

Application to personvernombud at Oslo University Hospital.

12.3 Informed Consent Procedure

The investigator is responsible for giving the subjects full and adequate verbal and written information about the nature, purpose, possible risk and benefit of the study. They will be informed as to the strict confidentiality of their patient data, but that their medical records may be reviewed for trial purposes by authorized individuals other than their treating physician.

It will be emphasized that the participation is voluntary and that the patient is allowed to refuse further participation in the protocol whenever she/he wants. This will not prejudice the patient's subsequent care. Documented informed consent must be obtained for all subjects included in the study before they are registered in the study. This will be done in accordance with the national and local regulatory requirements. The investigator is responsible for obtaining signed informed consent.

A copy of the patient information and consent will be given to the subjects. The signed and dated patient consent forms will be filed in the Investigator Site File binder and also scanned to be part of the patient's electronic medical record at the hospital.

12.4 Subject Identification

The investigator is responsible for keeping a list of all subjects (who have received study treatment or undergone any study specific procedure) including patient's date of birth and personal number, full names and last known addresses.

The patients will be identified in the CRFs by patient number, initials and date of birth.

13 TRIAL SPONSORSHIP AND FINANCING

The study is sponsored by funds from the Department of Anesthesiology, Oslo University Hospital.

14 TRIAL INSURANCE

For studies conducted in Norway: [name] has insurance coverage for the participants in this study through membership of the Drug Liability Association for the appropriate numbers included each year.

15 PUBLICATION POLICY

Upon study completion and finalization of the study report, the results of this study will either be submitted for publication and/or posted in a publicly assessable database of clinical study results.

The results of this study will also be submitted to the Competent Authority and the Ethics Committee according to EU and national regulations.

All personnel who have contributed significantly with the planning and performance of the study (Vancouver convention 1988) may be included in the list of authors.

